| 7. Smoking reduction in participants who did not achieve abstinence at 52-weeks | Self-reported daily cigarette consumption at 52 weeks post TQD reduced by at least 50% of baseline consumption accompanied by a CO reading at 52 weeks reduced by at least 50% compared to baseline. |

NB. Where participants have CO<10 at baseline and report 50% or more cigarette per day reduction at 52 weeks, sensitivity analyses will be carried out including and excluding them.

A sub-analysis of self-reported daily cigarette consumption at 52 weeks reduced by at least 50% of baseline consumption without accompanied CO readings will also be conducted.

Participants with missing data or who report being 'currently quit' at 52 weeks with no further data provided will be classified as non-reducers.

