Where a participant reports being 'currently quit' at 24 weeks post TQD, but has not been contactable to provide any other information, they will be counted as having smoked no more than 5 cigarettes since their last visit, and included as a 24 week sustained abstainer.

4. 7-day point prevalence
at 4-weeks post TQD

Definition: Not a single puff in the last 7-days

Data source: Q+4 CRF

If you have smoked since your last visit/contact, did you smoke at all in the last 7 days?

1. Yes
2. No

5. 7-day point prevalence
at 24-weeks post TQD

Definition: Not a single puff in the last 7-days

Data source: Q+24 CRF

If you have smoked since your last visit/contact, did you smoke at all in the last 7 days?

1. Yes
2. No

6. 7-day point prevalence
at 52-weeks post TQD

Definition: Not a single puff in the last 7-days

Data source: Q+52 CRF

Have you smoked at all in the last 7 days?

1. Yes
2. No

7. Smoking reduction in participants who did not achieve abstinence at 52 weeks

Definition: Daily cigarette consumption of at least 50% of baseline consumption accompanied by a CO reading of 50% of baseline

Data source: Q+52 Post Quit CRF

3b. How many cigarettes per day are you smoking now?

3c. Percentage reduction in number of cigarettes smoked from start of study

Q+52 Validation Visit CRF

3. Record carbon monoxide in expired breath (ppm)

NB. Where participants have CO<10 at baseline and report 50% or more cigarette per day reduction at 52 weeks post TQD, sensitivity analyses will be carried out including and excluding them.

A sub-analysis of self-reported daily cigarette consumption at 52 week follow up reduced by at least 50% of baseline consumption without accompanied CO readings will also be conducted.

Data source: Q+52 Post Quit CRF

3b. How many cigarettes per day are you smoking now?

3c. Percentage reduction in number of cigarettes smoked from start of study

8. Changes in urges to smoke and other tobacco withdrawal symptoms at 1 and 4 weeks.

Definition: Differences in the ratings of urge frequency at 1 and 4 weeks post quit on following scale: not at all, a little of the time, some of the time, a lot of time, almost all of the time, all of the time.

Differences in the ratings of urge strength at 1 and 4 weeks post quit on following scale: no urges, slight, moderate, strong, very strong, extremely strong.

Data source: Q+1 and Q+4 Post Quit CRF

Q6. How much of the time have you felt the urge to smoke over the past week?

1. Not at all

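### The low-baseline-CO sensitivity analysis of smoking reduction chooses whom to exclude partly by the outcome itself, and leaves the denominator unstated

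*SAP*

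**What the plan says.** In the SAP, under Definitions of smoking cessation and reduction outcomes (secondary outcome 7), a reducer must meet two conditions. One is the self-report component: "Self-reported daily cigarette consumption at 52 weeks post TQD reduced by at least 50% of baseline consumption". The other is that expired CO has at least halved between baseline and week 52.

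The note beneath sets up the sensitivity analysis. It concerns those whose baseline CO was below 10 and who "report 50% or more cigarette per day reduction at 52 weeks, sensitivity analyses will be carried out including and excluding them". Appendix 3, outcome 7, repeats the same joint condition ("Where participants have CO<10 at baseline and report 50% or more cigarette per day reduction at 52 weeks post TQD"), so it is not an isolated slip.

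Participants with missing data, or who say only that they have currently quit "at 52 weeks with no further data provided will be classified as non-reducers". No section defines the exclusion by baseline CO alone, and none says whether excluded participants leave the denominator.

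**The concern.** A cut-off on baseline CO suggests a worry about a baseline property: when CO is already low, a further halving is a weak or erratic confirmation of reduced smoking. The SAP does not give this reason; it is the natural inference from the threshold. A check on that worry would set aside everyone with low baseline CO and see whether the result holds.

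The stated rule sets aside only the low-CO participants who report the cut. Reporting the cut is necessary for success, so membership of the excluded set depends on a post-randomisation component of the outcome. If they are removed from the dataset, the low-CO participants left behind cannot contain a success. The low-CO group is then neither removed nor measured. A reader who sees lower rates in the excluding analysis could conclude that low-CO participants were driving the result when baseline CO had no influence at all.

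**Working it through.** The SAP gives no smoking-reduction rate, no share of participants with low baseline CO and no power for this outcome, so there is no planned figure to reproduce. All rates below are assumptions.

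**Step 1: what each reading computes.** Among the non-abstainers in one arm, let

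- n_H = participants with baseline CO of 10 or more, and H = those of them meeting both components;
- A = low-CO participants reporting the 50% cut, and S = those of A who also halve their CO;
- R = low-CO participants who report no such cut or have missing data;
- n = n_H + A + R.

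| Analysis | Rate |
|---|---|
| Including | (H + S) / n |
| Excluding, stated set removed | H / (n_H + R) |
| Excluding all with low baseline CO | H / n_H |
| Excluding, stated set kept but not counted as reducers | H / n |

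Nobody in R can be a success. So H/(n_H + R) is below H/n_H whenever H and R are both above zero. This needs no assumption about rates.

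**Step 2: size in a scenario where baseline CO is irrelevant.** Assume a reduction rate r of 20% in the NRT arm and 30% in the EC arm at every CO level, a low-CO share p of 10-25% in both arms, and every self-reported reducer meeting the CO criterion. Removing the stated set gives r(1 - p)/(1 - pr). The risk ratio is multiplied by (1 - 0.20p)/(1 - 0.30p).

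| p | NRT | EC | Difference (points) | RR |
|---|---|---|---|---|
| 10% | 0.18/0.98 = 18.4% | 0.27/0.97 = 27.8% | 9.5 | 1.52 |
| 20% | 0.16/0.96 = 16.7% | 0.24/0.94 = 25.5% | 8.9 | 1.53 |
| 25% | 0.15/0.95 = 15.8% | 0.225/0.925 = 24.3% | 8.5 | 1.54 |

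The including analysis, and exclusion of everyone with low CO, both give 20% v 30%, a difference of 10 points and RR 1.50. The fall ranges from 1.6 points (20 to 18.4) to 5.7 points (30 to 24.3). If both arms had the same true rate, the multiplier would be 1 and the risk ratio would stay at 1.

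If the stated set is kept but not counted as reducers, the rate is r(1 - p): 18% v 27%, 16% v 24% and 15% v 22.5% for the three shares. The RR is 1.50 each time.

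**Step 3: letting the CO criterion fail for some.** Assume 400 non-abstainers in an arm, 30% reporting the cut, and CO halved in half of those, whatever the baseline CO. With a 20% low-CO share, n_H = 320, H = 320 × 0.30 × 0.5 = 48, A = 80 × 0.30 = 24 and R = 56. Removal gives 48/376 = 12.8%, against 48/320 = 15.0% when all low-CO participants are excluded. At shares of 10% and 30% the stated rule gives 13.9% and 11.5%, again against 15.0%.

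**Step 4: against the SAP's own including analysis.** Removing A lowers the rate only if S/A exceeds (H + S)/n. That can fail. Take 400 participants, a 20% low-CO share, 40% reporting the cut, CO halved in 50% of reporters with higher baseline CO but in only 10% of low-CO reporters. Then H = 64, A = 32 and S = 3.2. Including gives 67.2/400 = 16.8%; removing the stated set gives 64/368 = 17.4%, a rise. Over 100,000 randomly drawn parameter sets, the stated rule always gave a lower rate than baseline-only exclusion, but was not lower than the including analysis in about 19%. That percentage depends on the ranges drawn and is not a probability for this trial.

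**The case against.** The strongest reply is that excluding need not mean deletion. The phrase sits in a note on how outcome 7 is classified, and can be read as counting these people, or not counting them, as reducers. The joint condition then makes sense: a low-CO participant who reports no 50% cut fails whatever the CO reading, so only self-reported reducers have a classification in doubt. The two analyses become an upper and a lower bound on a fixed denominator. This reading is plausible and the text does not rule it out. What remains of the point in that case is that the SAP must say which reading applies.

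A second reply is that the SAP never states the purpose of the check; it may be meant to show how far the result rests on reducers whose CO fall is hard to verify. That is fair, but a bound for that purpose needs the denominator kept, which is not stated.

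A third is that outcome 7 is already restricted to participants who did not achieve abstinence, so a baseline-only exclusion would not restore a fully randomised comparison. True, but it would avoid adding a second selection on the outcome.

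Finally, the result stands beside the including version and a self-report sub-analysis without CO, and Table 5 has no row for smoking reduction. This limits the consequence. The self-report sub-analysis drops the CO criterion for everyone, however, so it does not isolate low baseline CO.

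**Conclusion.** The point holds as a minor one. Under removal, the low-CO participants who remain have a success rate of zero by construction. The rate is below what baseline-only exclusion would give, and the analysis cannot separate an effect of low baseline CO from the effect of its own selection rule. In the scenario of Step 2, arm-level rates fall by about 2 to 6 points and the RR goes from 1.50 to 1.52-1.54; these figures rest wholly on assumed rates, equal low-CO shares in both arms, and every self-reported reducer passing the CO criterion.

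A reader might infer more: that the rule deletes successes and so must understate reduction, or that it distorts the treatment comparison. The SAP does not support either. Those removed are only potential successes, since some would fail the CO component, and Step 4 shows the rate can rise against the including analysis. The risk ratio barely moves under removal, and does not move in the Step 2 scenario if these participants are merely not counted as reducers. Neither the primary outcome nor the main analysis of smoking reduction is affected.

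**What to change.** In the note to secondary outcome 7 and in Appendix 3, outcome 7, define the set by baseline alone. Suggested wording: *a sensitivity analysis will exclude all participants with baseline CO <10 ppm in both arms, whatever they report at 52 weeks.* State the denominator alongside it.

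If a conservative bound is also wanted, specify it as a separate analysis: low-CO participants who self-report the reduction are recoded as non-reducers and kept in the denominator.

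The cost is a sentence or two in two places and a somewhat smaller sample in the exclusion analysis. No new data are needed, because a CO reading is already among the baseline variables.

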***See appendix 3 for how data for each outcome was collected**

Differences in tobacco withdrawal symptoms at 1 and 4 weeks.

Between-group differences in urges to smoke, and changes (from baseline) in tobacco withdrawal symptoms will be examined using ANOVA, in both the whole sample, and abstainers only sample.

Treatment ratings (e.g. satisfaction, taste, helpfulness, reasons for stopping product use)

Differences in mean ratings of treatment effects (product helpfulness, taste, satisfaction and reasons for stopping product use) between groups will be examined using ANOVA (or non-parametric tests where normality cannot be assumed) at 1 and 4 weeks post quit with adjustments where needed for normal distribution. NB. Where 2 NRT products were used and rated, the average rating of the two will be taken.

Adverse reactions (ARs)

The frequency of participants reporting each AR (nausea, sleep disturbance or throat/mouth irritation) at least once will be compared between arms using Chi squared test. The MedDRA coding system will be used.

Changes in respiratory problems

Frequency of respiratory problems at baseline and 12 month follow up will be compared between arms using Chi-squared test.

Cost-efficacy of the interventions.

The economic evaluation is conducted alongside the TEC trial by way of a cost-effectiveness analysis. Following NICE guidance, the analysis will be performed from the National Health Service (NHS) and Personal Social Services (PSS) perspective to reflect NHS England decision-making framework [16]. The analysis from a wider perspective will also be conducted to explore the possible societal impact of the intervention. All costs will be presented in 2015/16 Sterling Pounds (£). The objectives of the analysis are:

1. To assess cost-effectiveness of EC over and above UC at 12-month follow-up (primary outcome);
2. To estimate potential long term cost-effectiveness of the intervention.

These objectives will be achieved by combining data collected within the trial and existing models.

Costs estimation

Intervention cost

The intervention consists of six weekly sessions of standard SSS behavioural support for both arms, a starter kit of e-cigarette for the EC arm and supplies of NRT for the UC arm.

The second generation EC used in the trial contains 18mg/ml nicotine e-liquid, the cost of which will be recorded by the research team. The NRT supplies will also be recorded by the research team. The form and dosage of NRT will be matched to all the products with the same chemical name, dosage and form in Prescription Cost Analysis [17] to get the weighted average cost per item of each NRT product. The version of Prescription Cost Analysis will be for the appropriate financial year. Where the information on some aspects is missing (e.g. patches with no dosage recorded), the weighted average cost based on available information will be applied. Due to different approaches of dispensing NRT products between our research sites (direct dispense vs LOR), a conservative assumption is made that once an LOR is provided, the stated NRT products are considered dispensed. This is to avoid underestimating cost to the NHS.

The printing cost of accompanied information and instruction materials for both arms will also be recorded by the research team.

The sessions of behavioural support during the intervention period will be provided by the research team and stop smoking advisors. The attendance will be documented and the average wage rate of a qualified NHS Stop Smoking Service (SSS) advisor will be applied to the number of sessions attended.

Smoking cessation service after the intervention period

Smoking cessation services use after the intervention period, including pharmacotherapies and EC, will be recorded at 6 and 12 months follow up by self-report. The quantities reported will then be multiplied by the unit costs of corresponding services or net ingredient cost of prescribed items.

Health resources use

Participants' use of primary, secondary care and community services will be collected with self-report questionnaire at baseline, 6 and 12 month follow-up for the 6-month period prior to the follow-up. A set of national average costs of the appropriate year will be applied to the quantities reported to estimate the cost of health resources use [18, 19].

Quality of life

The EQ-5D [20] will be completed by patients at baseline, 6 and 12 months with the UK population tariff attributed to estimate utility values [21]. These utility values will then be used to calculate quality-adjusted life years (QALYs) using the area under the curve method [22].

Analysis

Basecase analysis

As the primary outcome will be 12-month sustained, biochemically validated abstinence, a cost-effectiveness analysis will be performed at this time point. The costs will include intervention cost, smoking cessation services cost after intervention period and health resources use cost that has occurred during the 12-month period. The difference in costs between arms will be controlled for health resources use at baseline, age, sex, study site, entitlement of free prescriptions, ethnicity and baseline FTCD. The quality adjusted life years (QALYs) will be calculated during the same time period. The difference in QALYs between arms will be controlled for utility value at baseline, age, sex, study site, entitlement of free prescriptions, ethnicity and baseline FTCD. Combining both, an incremental cost-effectiveness ratio (ICER) of cost per QALY will be calculated to assess the cost-effectiveness of the intervention, comparing with the standard care. The ICER will then be compared with the national willingness-to-pay threshold of £20,000-£30,000 per QALY gained [16].

Uncertainty assessment

The uncertainty around the decision to adopt the intervention will be assessed through a non-parametric bootstrap re-sampling technique. Bootstrapping has been proposed as an efficient approach for calculating the confidence limits for the ICER as its validity does not depend on any specific form of underlying distribution [23-26]. A cost effectiveness acceptability curve (CEAC) will be plotted based on the outcomes of the 5000 bootstrap iterations [27].

A separate sensitivity analysis will be carried out to examine the impact of the assumption of LOR equating dispense on the intervention costs. This will be undertaken by using the actual quantities used reported by the participants as the cost base of the NRT costs. A set of weighted average cost per unit of the NRT products will be extracted from Prescription Cost Analysis [17] with the same approach as in the base case analysis. These unit costs will then be multiplied by the quantities reported of corresponding NRT products.

Given that the current practice for smoking cessation does not provide prescription of EC while allows prescription of pharmacotherapies, a separate analysis will be carried out, including participants' out-of-pocket money for EC and pharmacotherapies, to examine the possible cost-shift from NHS to smokers.

Handling missing data

For the smoking cessation services use after intervention and health resources use, it will only be deemed as missing when all sections under one question are left blank. For instance, where one question has five sub-questions (annotated as a), b), c), etc.), all five will be deemed as missing when all five are left blank. If one of them is answered, the others will be assumed as 0. For EQ-5D-5L, due to the structure of the questionnaire, the whole section is considered missing if any of the five questions is not answered. The missing data in services use and EQ-5D-5L will be imputed using Rubin's multiple imputation method [28].

To assess the impact of the missing data, an additional set of analyses will be carried out using the complete case analysis (CCA), whereby results are analysed only for those participants who had both the completed cost and outcome data at all time points [29-32].

Long term cost and outcome projections

[figure not shown]
As the impact of smoking cessation is recognised to be life-long, we will investigate the use of existing models to project the impact of the intervention in a longer term. These models would enable the estimation of the potential long-term health care cost savings from smokers quitting smoking as a result of the intervention. These will be combined with longer term health utilities from published studies according to smoking status. The combination of trial data and health utility data will provide inputs to a longer term health economic model to estimate the longer term QALYs and cost per QALY gained.

Figures

Participant flow

Participant throughput will be summarized in a CONSORT diagram (see figure 1).

Figure 1: Consort Diagram

Patients included in the analysis for the primary outcome (N=XX)
Participant deaths (N=XX)
Participants who moved to untraceable address (N= XX)
Participants who withdrew and refused follow up (N=XX)
Participants who withdrew and permitted follow up (N=XX)

Patients included in the analysis for the primary outcome (N=XX)
Participant deaths (N=XX)
Participants who moved to untraceable address (N= XX)
Participants who withdrew and refused follow up (N=XX)
Participants who withdrew and permitted follow up (N=XX)

Survival curve

We will use Cox's proportional hazards model to compare time to relapse in the two conditions'.

Tables

Table 1 - Baseline measurements

	NRT (N=XXX)	EC (N=XXX)
Age (years) – mean (SD)		
Female – no. (%)		
Marital status – no. (%)		
Single		
Separated or divorced		
Married		
Widowed		
Ethnicity – no. (%)		
White British		
White other		
Black		
Asian		
Mixed		
Other		
Educational qualification – no. (%)		
Primary school		
Secondary school		
Further education/diploma		
Higher education		
Employment status – no. (%)		
In paid employment		
Entitled to free prescriptions – no. (%)		
Smoking and quitting history		
Cigarettes smoked per day – Mean (SD)		

Baseline CO – Mean (SD)		
FTCD – Mean (SD)		
Past use of stop smoking aids – N (%) Nicotine replacement therapy Champix Zyban Electronic cigarettes		
Age when started smoking – Mean (SD)		
Spouse or partner smokers – N (%)		
Study Site – no. (%)		
London		
Leicester		
East Sussex		

Table 2 – Participant adherence and contamination

	NRT (n=...)	EC (n=...)	P value	Mean difference (95% CI)
Number of contacts completed ^a (max 5 – preparation, W1, w4, 6M, 12M) – mean (SD)				

Use of allocated product over the initial 4 weeks:
 
On how many days used (0-28): Mean (SD)
 
% using daily
 
Use of allocated products at 6M:
 
Length of allocated product use in weeks (0-26): Mean (SD)
 
% using currently (at least once a week)
 
Use of allocated products at 12M:
 
Length of allocated product use in weeks (0-26): Mean (SD)
 
% using currently (at least once a week)
 
Length of allocated product use in weeks (0-52) for those with complete 4 week, 6 and 12 month data: Mean (SD)
 
Products used in those still using at 12M (type of NRT or type of EC) N (%)
				

No. mls/cartridges/pieces/sprays of allocated product used per day – mean (SD)
 
1 week post quit
 
4 weeks post quit
 
24 weeks post quit
 
52 weeks post quit
			N/A	

Tried non-allocated product within the initial 4 weeks N (%): Used for 5 or more consecutive days, N (%)
 
Use of non-allocated products at 6M (excludes initial 4 weeks): Length of non-allocated product use in weeks (0-22): Mean (SD)
 
Use of non-allocated products at 12M (excludes initial 4 weeks): Length of non-allocated product use in weeks (0-22): Mean (SD)
 
Length of non-allocated product use in weeks (0-48) for those with complete 6 and 12 month data: Mean (SD)
				

Reason for stopping allocated product use in those not using it in the initial 4 weeks, N (%)
 
Cost Did not like the taste Adverse reaction Not satisfying Difficult to use Embarrassing to use Difficult to obtain them Smoking normal cigarettes now To quit nicotine Other reason
				

Any use of other products (including single use), N (%)
 
Varenicline Bupropion
				

^a Includes those who completed and part completed sessions over the telephone

Table 3 – Choice of product

Type of NRT selected, N (%) Using combination, N (%)
		

Switched to different NRT product in first 4 weeks N (%)
		

Type of EC used (cartridge based or refillable), N (%) 1 week post quit 4 weeks post quit 24 weeks post quit 52 weeks post quit
		

Switched to different EC in first 4 weeks N (%)
		

E-liquid used
		

Nicotine strength – mean (SD) 1 week post quit 4 weeks post quit 24 weeks post quit 52 weeks post quit
		

Flavours, N (%) 1 week post quit 4 weeks post quit 24 weeks post quit 52 weeks post quit
	
Tobacco Fruit Menthol/mint Tobacco menthol Vanilla Chocolate, dessert. Sweet or candy flavor No flavor Coffee Alcoholic drink Energy or soft drink Other Don't know
	

Given additional e-liquid at 2 weeks post-TQD, N (%) Purchased additional e-liquid at 2 weeks post-TQD, N (%)
		

Table 4 – Helpfulness, taste, and satisfaction of product

Rating	EC (n=...)	NRT (n=...)	P value	Mean difference (95% CI)
Helpfulness ^a , mean (SD) 1 week post quit 4 weeks post quit				
Taste compared to normal cigarettes, mean (SD) 1 week post quit 4 weeks post quit				
Satisfaction compared to normal cigarettes, mean (SD) 1 week post quit 4 weeks post quit				

^aWhere 2 NRT products were used and rated, the average rating of the two was taken.

Table 5 – Results for primary and secondary outcomes – unadjusted, using chi-square test; adjusted, using binomial regression

	NRT (n=...)	EC (n=...)	Unadjusted Relative Risk (95% CI)	Unadjusted P-value	Adjusted Relative Risk (95% CI)	Adjusted P-value
Primary outcome						
CO validated sustained abstinence at 52 weeks post TQD, N (%)						
Secondary Outcomes						
CO validated sustained abstinence between 24 and 52 weeks post TQD, N (%)						
CO validated sustained abstinence at 4 weeks post TQD, N (%)						
Sustained abstinence at 24 weeks post TQD, N (%)						
7-day point prevalence at 4 weeks post TQD, N (%)						
7-day point prevalence at 24 weeks post TQD, N (%)						
7-day point prevalence at 52 weeks post TQD, N (%)						

Table 6 – Change in respiratory symptoms

	NRT (N=)		EC (N=)		P-value	Odds Ratio (95% CI)
	Baseline N (%)	12 months N (%)	Baseline N (%)	12 months N (%)		
Shortness of breath						
Wheezing						
Cough						
Phlegm						

Table 7– Percentage participants reporting an adverse reaction at least once

% (N) reporting Adverse Reaction	EC	NRT	P-value
Nausea			
Sleep disturbances			
Throat/mouth irritation			

Table 8 – Differences in urges to smoke at 1 and 4 weeks post quit (abstainers only)

Symptom	1 week post quit		P-value	Mean difference (95% CI)	4 weeks post quit		P-value	Mean difference (95% CI)
	EC	NRT			EC	NRT		
Frequency of urge to smoke – mean (SD)								
Strength of urge to smoke – mean (SD)								
Composite urge score – mean (SD)								

Table 9 – Differences in urges to smoke at 1 and 4 weeks post quit (whole sample)

Symptom	1 week post quit		P-value	Mean difference (95% CI)	4 weeks post quit		P-value	Mean difference (95% CI)
	EC	NRT			EC	NRT		
Frequency of urge to smoke – mean (SD)								
Strength of urge to smoke – mean (SD)								
Composite urge score – mean (SD)								

Table 10 – Change in withdrawal symptoms between baseline and 4-weeks post TQD (abstainers only)

Symptom	NRT (n=)	EC (n=)	P-value	Mean difference, (95% CI)
Depressed – mean (SD)				
Irritable – mean (SD)				
Restless – mean (SD)				
Hungry – mean (SD)				
Poor concentration – mean (SD)				
Composite MPSS score – mean (SD)				

Table 11 – Change in withdrawal symptoms between baseline and 4-weeks post TQD (whole sample)

Symptom	NRT (n=)	EC (n=)	P-value	Mean difference (95% CI)
Depressed – mean (SD)				
Irritable – mean (SD)				
Restless – mean (SD)				
Hungry – mean (SD)				
Poor concentration – mean (SD)				
Composite MPSS score – mean (SD)				

Health economics tables

Table 12: Breakdown of intervention cost (mean [S.D.])

Cost item	NRT (n=xxx)	EC (n=xxx)
Behavioural support sessions		
NRT/EC supplies		
Information sheets		
Total		

Table 13: Unit cost

Services	Unit cost	Sources
Smoking cessation help		
GP		
NHS SSS		
NHS Smoking Helpline service		
Pharmacotherapies		
Patch		
Gum		
Microtab		
Inhaler		
Lozenge		
Spray		
Mouthstrip		
Varenicline		
Bupropion		
Health resources use		
A & E		
Outpatient		
Inpatient		
Day case		
Emergency ambulance		

GP (in office)		
Practice nurse (in office)		
GP (home visit)		
Practice nurse (home visit)		
Prescription		

Table 14: Usage and mean cost of services (mean [S.D.]

Services	NRT			EC		
	Baseline	Six months	12 months	Baseline	Six months	12 months
Smoking cessation help	n=xxx	n=xxx	n=xxx	n=xxx	n=xxx	n=xxx
GP						
NHS SSS						
NHS Smoking Helpline service						
Cost of smoking cessation help	£xx (£xx)	£xx (£xx)	£xx (£xx)	£xx (£xx)	£xx (£xx)	£xx (£xx)
Pharmacotherapies	n=xxx	n=xxx	n=xxx	n=xxx	n=xxx	n=xxx
Patch						
Gum						
Microtab						
Inhaler						
Lozenge						
Spray						
Mouthstrip						
Varenicline						
Bupropion						
Cost of pharmacotherapies	£xx (£xx)	£xx (£xx)	£xx (£xx)	£xx (£xx)	£xx (£xx)	£xx (£xx)
Health resources use	n=xxx	n=xxx	n=xxx	n=xxx	n=xxx	n=xxx
A & E						
Outpatient						
Inpatient						
Day case						
Emergency ambulance						

GP (in office)						
Practice nurse (in office)						
GP (home visit)						
Practice nurse (home visit)						
Prescription						
Cost of health resources use	£xx (£xx)	£xx (£xx)	£xx (£xx)	£xx (£xx)	£xx (£xx)	£xx (£xx)

Table 15: Utility values derived from EQ-5D (mean [S.D.]

	NRT		EC	
Baseline	n=xxx		n=xxx	
Six months	n=xxx		n=xxx	
12 months	n=xxx		n=xxx	

Table 16: Missing data table for imputation

Variables	Number of missing values	Proportion of missing values
Age		
Gender		
Study site		
Entitlement of free prescriptions		
Ethnicity		
Baseline FTCD		
Baseline smoking cessation help cost		
Six months smoking cessation help cost		
12 months smoking cessation help cost		
Baseline pharmacotherapies cost		
Six months pharmacotherapies cost		
12 months pharmacotherapies cost		
Baseline health resources cost		
Six months health resources cost		
12 months health resources cost		
Intervention cost		
Baseline EQ-5D index		
Six months EQ-5D index		
12 months EQ-5D index		

12 months validated abstinence		
--------------------------------	--	--

Table 17: Basecase result (mean [S.E.] / [95% CI])

	NRT (n=xxx)	EC (n=xxx)
Intervention cost		
Smoking cessation help cost in the six months prior to baseline		
Pharmacotherapies cost in the six months prior to baseline		
Health resources use cost in the six months prior to baseline		
Health care cost in the six months prior to baseline		
Smoking cessation help cost in the six months post quit date		
Pharmacotherapies cost in the six months post quit date		
Health resources use cost in the six months post quit date		
Health care cost in the six months post quit date		
Smoking cessation help cost from six months to 12 months post quit date		
Pharmacotherapies cost from six months to 12 months post quit date		
Health resources use cost from six months to 12 months post quit date		
Health care cost from six months to 12 months post quit date		
Total costs during the trial period		
Unadjusted difference in total costs during the trial period		

Adjusted difference in total costs during the trial period		
EQ-5D index at baseline		
EQ-5D index at six months post quit date		
EQ-5D index at 12 months post quit date		
QALYs during the trial period		
Unadjusted difference in QALYs during the trial period		
Adjusted difference in QALYs during the trial period		
ICER at 12 months post quit date		

Table 18: Complete case analysis results (mean [S.D.] / [95% CI])

	NRT (n=xxx)	EC (n=xxx)
Intervention cost		
Smoking cessation help cost in the six months prior to baseline		
Pharmacotherapies cost in the six months prior to baseline		
Health resources use cost in the six months prior to baseline		
Health care cost in the six months prior to baseline		
Smoking cessation help cost in the six months post quit date		
Pharmacotherapies cost in the six months post quit date		
Health resources use cost in the six months post quit date		
Health care cost in the six months post quit date		

Smoking cessation help cost from six months to 12 months post quit date		
Pharmacotherapies cost from six months to 12 months post quit date		
Health resources use cost from six months to 12 months post quit date		
Health care cost from six months to 12 months post quit date		
Total costs during the trial period		
Unadjusted difference in total costs during the trial period		
Adjusted difference in total costs during the trial period		
EQ-5D index at baseline		
EQ-5D index at six months post quit date		
EQ-5D index at 12 months post quit date		
QALYs during the trial period		
Unadjusted difference in QALYs during the trial period		
Adjusted difference in QALYs during the trial period		
ICER at 12 months post quit date		

Table 19: Participants out-of-pocket cost (mean [S.D.]

	NRT (n=xxx)	EC (n=xxx)
E-cigarettes		
Pharmacotherapies		
Total costs to the NHS		

References

